2.2. Study Objectives and Endpoints

[Table 1](#) presents the objectives and endpoints.

Table 1: Objectives and Endpoints

Objectives	Endpoints
Primary	
To evaluate and compare the efficacy of parsaclisib plus ruxolitinib versus placebo plus ruxolitinib on spleen volume at Week 24.	Proportion of participants achieving $\geq 35\%$ reduction in spleen volume from baseline to Week 24 as measured by MRI (or CT scan in applicable participants).
Secondary	
To evaluate and compare the effect of parsaclisib plus ruxolitinib versus placebo plus ruxolitinib on participant reports of MF symptoms.	Proportion of participants who have a $\geq 50\%$ reduction in TSS from baseline to Week 24 as measured by the MFSAF v4.0 diary. Change in TSS from baseline to Week 24 as measured by the MFSAF v4.0 diary. Time to the first $\geq 50\%$ reduction in TSS as measured by the MFSAF v4.0 diary.
To evaluate and compare the effect of parsaclisib plus ruxolitinib versus placebo plus ruxolitinib with respect to OS.	OS determined from the date of randomization until death due to any cause.
To evaluate and compare the safety and tolerability of parsaclisib plus ruxolitinib versus placebo plus ruxolitinib.	Safety and tolerability will be assessed by monitoring the frequency and severity of AEs, performing physical examinations, and evaluating changes in vital signs, ECGs, and laboratory results.
To evaluate and compare the time to onset or response and duration of response in spleen volume of participants receiving parsaclisib plus ruxolitinib versus placebo plus ruxolitinib.	Time of onset of a $\geq 35\%$ reduction in spleen volume and duration of maintenance of a $\geq 35\%$ reduction in spleen volume.
[REDACTED]	

Table 1: Objectives and Endpoints (Continued)

Objectives	Endpoints

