OS adjusted for crossover using rank preserving structural failure time	Inference: Cox regression model including treatment group, baseline (or screening, if applicable) platelet count ($\geq 100 \times 10^9/L$ vs 50 to $< 100 \times 10^9/L$ inclusive), and DIPSS category (intermediate-1 vs intermediate 2 vs high) at randomization	ITT	S
Time to the first $\geq 35\%$ reduction in spleen volume	Inference: Log-rank test with stratification of baseline (or screening, if applicable) platelet count ($\geq 100 \times 10^9/L$ vs 50 to $< 100 \times 10^9/L$ inclusive) and DIPSS (intermediate-1 vs intermediate-2 vs high) at randomization Estimation: Kaplan-Meier	ITT	P
Duration of maintenance of a $\geq 35\%$ reduction in spleen volume	Estimation: Kaplan-Meier	ITT with spleen response	P

Other secondary endpoints, including change and percentage change in MFSAF TSS over time from baseline to Week 24 as measured by the MFSAF v4.0 diary, will be summarized descriptively by treatment group.

For the stratifications of platelet and DIPSS, within a platelet category, in the event that a particular DIPSS stratification level has fewer than 30 participants randomized, it will be combined with the nearest adjacent DIPSS level (eg, Intermediate-1 vs Intermediate-2 vs High). For example, if too small, Intermediate-1 or High risk will be merged with Intermediate-2. If Intermediate-2 has too few participants, then it will be merged with the smaller of the 2 adjacent strata.

In the event that 2 DIPSS stratification levels are combined, a sensitivity analysis for the primary endpoint without combining levels will be conducted.

The primary endpoint will also be compared between treatment groups within each of the following subgroups:

- Baseline platelet count ($\geq 100 \times 10^9/L$ vs 50 to $<100 \times 10^9/L$ inclusive) (Note that if a participant's platelet count is $< 50 \times 10^9/L$ at baseline, the platelet count at screening will be used instead)
- DIPSS category (Intermediate-1 vs Intermediate-2 vs High)
- Sex: male and female
- Age group: ≤ 65 years or > 65 years
- MF type: PMF or PPV-MF/PET-MF
- Presence/absence of V617F mutation at baseline
- Presence/absence of HMR mutations at baseline
- Baseline spleen volume group: \leq median or $>$ median
- Baseline spleen palpation size group: ≤ 10 cm or > 10 cm
- Race: white/Caucasian, black/African American, Asian, American Indian/Alaska Native, Native Hawaiian/Pacific Islander, or other

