3.3. Sample Size Considerations

The primary endpoint of this study is the proportion of participants with $\geq 35\%$ spleen volume reduction from baseline to Week 24 as measured by MRI (or CT scan in applicable participants). The primary endpoint will be analyzed by CMH test stratified by DIPSS category (intermediate-1 vs intermediate-2 vs high) and baseline platelet count ($\geq 100 \times 10^9/L$ vs 50 to $< 100 \times 10^9/L$ inclusive). Assuming a 58.2% (29.4%) response rate for participants with normal (low) platelet count for the ruxolitinib plus parsaclisib group versus 41.0% (17.2%) response rate for participants with normal (low) platelet count for the ruxolitinib plus placebo group, to achieve 83.67% power to detect a statistically significant difference with a 2-sided Type I error of 5%, a sample size of 440 participants is required to be randomized equally between treatment groups.

For the key secondary endpoint of proportion of participants who have a $\geq 50\%$ in MFSAF TSS from baseline to Week 24, assuming a response rate of 61.7% (50.0%) for participants with

normal (low) platelet count for the ruxolitinib plus parsaclisib group and a response rate of 45.9% (34.5%) for participants with normal (low) platelet count for the ruxolitinib plus placebo group, a sample size of 440 will provide 80.02% power using CMH test given a 2-sided Type I error of 5%.

A test for OS will be performed when 85 deaths are observed using the log-rank test stratified by platelet count and DIPSS category at baseline at a 2-sided Type I error level of 0.05. The log-rank test will provide 80% power to detect a hazard ratio of 0.54. Assuming a median survival time of 5.3 years for ruxolitinib plus placebo and enrollment duration is 1.5 years, the expected time to analysis from the first participant randomized is 3 years.

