7.4.1.2. Duration of Maintenance of a $\geq 35\%$ Reduction in Spleen Volume

The duration of $\geq 35\%$ reduction from baseline in spleen volume is defined as the interval between the first spleen volume measurement that is $\geq 35\%$ reduction from baseline and the date of the first measurement that is no longer a $\geq 35\%$ reduction from baseline. If the end date is not observed before the database cutoff, the duration will be censored at the last assessment.

The endpoint will be derived for participants who were randomized and who had at least 1 measurement of $\geq 35\%$ reduction from baseline.

Kaplan-Meier estimates of median duration with 95% CIs will be provided.

The ITT population with spleen volume response before crossover will be used.

A supportive analysis for duration of $\geq 35\%$ reduction from baseline in spleen volume defined as the interval between the first spleen volume measurement that is $\geq 35\%$ reduction from baseline and the date of the first measurement that is no longer a $\geq 35\%$ reduction from baseline that is also a $> 25\%$ increase from nadir will be provided.

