2.2 Secondary Efficacy			
2.2.1.1	Time to the First $\geq 35\%$ Reduction in Spleen Volume	ITT	
2.2.1.2	Duration of Maintenance of a $\geq 35\%$ Reduction in Spleen Volume	ITT With Spleen Volume Response	
2.2.1.3	Time From the First $\geq 35\%$ Reduction in Spleen Volume to Loss of $\geq 35\%$ Reduction in Spleen Volume With a $\geq 25\%$ Spleen Volume Increase From Nadir	ITT With Spleen Volume Response	
2.2.1.4	Summary of Spleen Volume by Visit	ITT	
2.2.2.1	Cochran-Mantel-Haenszel Test of Proportion of Participants With $\geq 50\%$ Reduction in MFSAF v4.0 Total Symptom Score at Week 12 and Week 24	ITT	
2.2.2.2	Cochran-Mantel-Haenszel Test of Proportion of Participants With $\geq 50\%$ Reduction in MFSAF v4.0 Total Symptom Score at Week 12 and Week 24	PP	
2.2.2.3	Time to the First $\geq 50\%$ Reduction in MFSAF v4.0 Total Symptom Score	ITT	
2.2.2.4	Summary of MFSAF v4.0 Total Symptom Score Using 7-Day Window by Visit	ITT	
2.2.2.5.1	Summary of MFSAF v4.0 Individual Symptom Scores by Visit – Fatigue	ITT	
2.2.2.5.2	Summary of MFSAF v4.0 Individual Symptom Scores by Visit – Night Sweats	ITT	
2.2.2.5.3	Summary of MFSAF v4.0 Individual Symptom Scores by Visit – Itchiness	ITT	
2.2.2.5.4	Summary of MFSAF v4.0 Individual Symptom Scores by Visit – Abdominal Discomfort	ITT	

Table No.	Title	Population	Standard
2.2.2.5.5	Summary of MFSAF v4.0 Individual Symptom Scores by Visit – Pain Under Left Ribs	ITT	
2.2.2.5.6	Summary of MFSAF v4.0 Individual Symptom Scores by Visit – Early Satiety	ITT	
2.2.2.5.7	Summary of MFSAF v4.0 Individual Symptom Scores by Visit – Bone Pain	ITT	
2.2.2.6	Summary of MFSAF v4.0 Spleen-Related Symptom Scores by Visit	ITT	
2.2.2.7.1	Overall Survival	ITT	
2.2.2.7.2	Overall Survival	PP	
2.2.2.7.3	Overall Survival Adjusted by Rank Preserving Structural Failure Time	ITT	

Table No.	Title	Population	Standard
Safety			

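### Duration of spleen response is to be compared between arms, but both planned duration analyses describe responders only, so the medians are not a randomized comparison

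*SAP*

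**What the plan says.** SAP Table 1 and Protocol Table 7 state the objective as "To evaluate and compare the time to onset or response and duration of response in spleen volume of participants receiving parsaclisib plus ruxolitinib" against placebo plus ruxolitinib. It covers two endpoints, time to onset and duration of maintenance of a reduction of at least 35%.

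For duration, SAP 7.4.1.2 says "The endpoint will be derived for participants who were randomized and who had at least 1 measurement of" a reduction of that size, and "The ITT population with spleen volume response before crossover will be used". The output is limited to medians: "Kaplan-Meier estimates of median duration with 95% CIs will be provided". On follow-up: "If the end date is not observed before the database cutoff, the duration will be censored at the last assessment". A supportive version changes the definition of loss of response by also requiring a rise from nadir, but it covers the same responders.

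Protocol Table 17 marks duration as a primary-type analysis (P), gives the population as "ITT with spleen response" and lists estimation only, with no inference line. In SAP Appendix A, Tables 2.2.1.2 and 2.2.1.3 both carry the population "ITT With Spleen Volume Response".

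SAP 3.2 analyzes secondary endpoints only if the primary succeeds. It also says that secondary endpoints outside the fixed sequence will be tested at a two-sided 5% level without alpha control.

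**The concern.** Randomization balances all randomized participants. It does not balance those who later respond, because response is an outcome that the experimental drug is meant to change. If parsaclisib succeeds, its responder group includes people who would not have responded on ruxolitinib alone, while the placebo group contains only those who respond without help. If the added responders lose response sooner, they pull the parsaclisib median down even when nobody's response has been shortened. Complete follow-up does not remove this, since it comes from who is in the analysis and not from censoring.

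At stake is the answer to a stated comparative objective. Readers will set the two medians beside each other, and the plan offers no all-randomized estimate of duration to set against them.

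**Working it through.** **Onset and duration side by side.** Time to first response uses the full ITT population and a stratified log-rank test (SAP 7.4.1.1). Duration uses responders, Kaplan-Meier medians and no test (SAP 7.4.1.2). Other all-randomized spleen outputs in Appendix A are the CMH tests of response at Weeks 12 and 24 (Table 2.1.1.1), spleen volume by visit (Table 2.2.1.4) and a plot of reductions of at least 25% (Figure 4.2.4). None measures how long a reduction of at least 35% is maintained.

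**The plan's own figure.** No figure is given for duration. The response rates come from SAP 3.3: "Assuming a 58.2% (29.4%) response rate for participants with normal (low) platelet count for the ruxolitinib plus parsaclisib group versus 41.0% (17.2%) response rate" on placebo. They are Week 24 rates, and the stated power is 83.67% with 440 participants. The platelet mix is not stated. With 0% to 30% low platelets (assumed), the final test alone has 95.3% to 93.4% power. Requiring Z > 0.18 at 100 participants, Z > 1.28 at 220 and Z > 1.96 at 440, and treating Week 12 and Week 24 effects as equal, a simulation gives 85.2% to 81.9%, and 83.6% at 15% low platelets. The stated figure is thus reproduced once the interim stops are counted, and the rates can be used as design inputs.

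**Share of added responders.** Two assumptions are needed: Week 24 response stands in for ever having responded, and every placebo responder would also respond on parsaclisib.

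- Normal platelets: (58.2 − 41.0)/58.2 = 29.6% of parsaclisib responders.
- Low platelets: (29.4 − 17.2)/29.4 = 41.5%.
- With no low-platelet participants, expected responders per arm of 220 are 0.582 × 220 = 128 and 0.410 × 220 = 90.

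**Responder-only median, normal platelets.** Assume exponential durations, with a 24-month median for common responders in both arms and a median of *a* months for added responders. The parsaclisib median *t* solves

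(41.0/58.2) × 2^(−t/24) + (17.2/58.2) × 2^(−t/a) = 0.5

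- a = 6: t = 15.5 months.
- a = 12: t = 19.3 months.
- a = 24: t = 24.0 months, equal to placebo.

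The low-platelet rates give 12.7 (a = 6) and 17.7 (a = 12) against 24.0.

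**Mean time in response per randomized participant, normal platelets.** Over 12 months from response onset, a group with median *m* spends on average R(m) = (m/ln 2) × (1 − 2^(−12/m)) months in response: R(24) = 10.14, R(12) = 8.66, R(6) = 6.49. Nonresponders count zero.

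- Placebo: 0.410 × 10.14 = 4.2 months.
- Parsaclisib, a = 6: 4.16 + 0.172 × 6.49 = 5.3 months.
- Parsaclisib, a = 12: 4.16 + 0.172 × 8.66 = 5.6 months.

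If the 12 months run from randomization and every response starts at the first scheduled scan (Week 12), the figures are 4.3 to 4.6 against 3.3. The direction is the same.

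**Sensitivity.** If parsaclisib also lengthens the common responders' median by 25% (to 30 months), the responder-only median is 18.1 to 22.5 months, still below 24.0. With a 50% gain (to 36 months) and a = 12, it is 25.4, above 24.0. Reversal therefore depends on durations that the documents do not supply.

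**The case against.** The best defense is that the plan hardly makes the comparison. Protocol Table 17 gives an inference line for onset and none for duration, and SAP 7.4.1.2 stops at medians with confidence intervals. A reader might infer that an invalid test is specified; the duration section specifies none. Duration is also outside the alpha-controlled sequence. This stands and limits the severity. It does not settle the matter, because the objective says compare, Table 17 marks the analysis P, and SAP 3.2 says such endpoints will be tested.

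A reader might also infer that about 30% of parsaclisib responders are known to owe their response to the drug. The documents do not support that. The rates are for Week 24, whereas the duration set is anyone with one qualifying scan before crossover, and the overlap between arms is an assumption. That parsaclisib enlarges the group is the design hypothesis, although duration is analyzed only after a significant primary result.

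The third objection is practical. Late enrollees may have little beyond the Week 12 and Week 24 scans before study-wide crossover, so a very short common horizon would nearly repeat the primary endpoint and a longer one must handle censoring. This is correct, and the remedy has to address it. Finally, exploratory sections are redacted, so an all-randomized duration analysis there cannot be ruled out; none appears in the visible table list.

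**Conclusion.** The point holds as a gap between objective and analysis. The plan sets out to compare duration, and both visible duration analyses condition on a post-randomization outcome that will differ between arms whenever the primary succeeds.

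The tempting stronger reading is that the trial will report a shorter duration for the better arm. The documents do not support it. They contain no duration data and nothing to show that added responders relapse sooner. The 15.5 to 19.3 against 24.0 months illustrates what can happen under exponential durations, full overlap of responders and assumed medians. It is not a forecast.

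The endpoint is not a key secondary and has no test in its own section, so this is a worthwhile and inexpensive improvement. It does not threaten the primary conclusion.

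**What to change.** In SAP 7.4.1.2 and Protocol Table 17:

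- Add an all-randomized between-arm analysis: the probability of being in response (reduction of at least 35%) over time, and the restricted mean time in response to a prespecified week, with nonresponders contributing zero. Report the stratified difference with a 95% CI.
- Name a censoring-aware estimator, such as a multistate estimate or the difference between the Kaplan-Meier curves for onset and for loss of response, with administrative censoring at study-wide crossover.
- Count death, treatment discontinuation and early crossover as out of response. This matches SAP 7.3.1, where discontinuation, early crossover or a missing Week 24 scan is nonresponse.
- Fix the week with follow-up in mind. With the SAP's 1.5-year enrollment (78 weeks, assumed uniform) and crossover opening when the last participant reaches Week 24, (78 − 24)/78 = 69% of participants could be followed to Week 48 and (78 − 48)/78 = 38% to Week 72, ignoring data-cleaning time.
- Keep the responder-only medians, labeled as within-arm description and not a between-arm comparison, and reconcile this with the testing sentence in SAP 3.2.

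The cost is SAP and protocol wording plus one table and one figure, from scans already scheduled every 12 weeks to Week 144. No participants or procedures are added. The drawbacks are a less familiar summary and limited information at later weeks for late enrollees.

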3. STUDY DESIGN

3.1. Randomization

Participants will be randomized 1:1 to parsaclisib plus ruxolitinib and placebo plus ruxolitinib with stratification for DIPSS risk category (intermediate-1 vs intermediate-2 vs high) and baseline platelets ($\geq 100 \times 10^9/L$ vs 50 to $< 100 \times 10^9/L$ inclusive). Note that if a participant's platelet count is $< 50 \times 10^9/L$ at baseline, the platelet count at screening will be used for stratification/randomization.

3.2. Control of Type I Error

This study defines a single primary endpoint with a single primary analysis. The study will be claimed to have achieved the primary efficacy objective when the primary endpoint shows a significant result at 2-sided alpha of 0.05 at final analysis. The secondary efficacy endpoints will be analyzed only when the study has reached the efficacy objective in the primary endpoint. The key secondary efficacy variables will be tested following a fixed-sequence-testing procedure with each at the 2-sided alpha level of 0.05 in the order below:

1. The proportion of participants who have a $\geq 50\%$ reduction from baseline to Week 24 in MFSAF TSS
2. Overall survival

Other secondary [REDACTED] endpoints will be tested using a 2-sided, 5% significance level; however, these are not considered alpha-controlled hypotheses.

There are 2 planned interim analyses in this study, both aiming to terminate the study if there is inadequate efficacy. The nonbinding futility rules in Interim Analyses 1 and 2 will control the probability of continuing beyond Interim Analysis 2 at 10%. As no formal decision for efficacy will be made based on these interim analyses, no overall alpha will be spent.

An independent DMC will be assembled to monitor safety data, efficacy data, and study conduct on a regular and ongoing basis during the study. See Section 10 for details regarding the alpha-spending plan and interim analyses conducted in this study.

3.3. Sample Size Considerations

The primary endpoint of this study is the proportion of participants with $\geq 35\%$ spleen volume reduction from baseline to Week 24 as measured by MRI (or CT scan in applicable participants). The primary endpoint will be analyzed by CMH test stratified by DIPSS category (intermediate-1 vs intermediate-2 vs high) and baseline platelet count ($\geq 100 \times 10^9/L$ vs 50 to $< 100 \times 10^9/L$ inclusive). Assuming a 58.2% (29.4%) response rate for participants with normal (low) platelet count for the ruxolitinib plus parsaclisib group versus 41.0% (17.2%) response rate for participants with normal (low) platelet count for the ruxolitinib plus placebo group, to achieve 83.67% power to detect a statistically significant difference with a 2-sided Type I error of 5%, a sample size of 440 participants is required to be randomized equally between treatment groups.

For the key secondary endpoint of proportion of participants who have a $\geq 50\%$ in MFSAF TSS from baseline to Week 24, assuming a response rate of 61.7% (50.0%) for participants with

normal (low) platelet count for the ruxolitinib plus parsaclisib group and a response rate of 45.9% (34.5%) for participants with normal (low) platelet count for the ruxolitinib plus placebo group, a sample size of 440 will provide 80.02% power using CMH test given a 2-sided Type I error of 5%.

A test for OS will be performed when 85 deaths are observed using the log-rank test stratified by platelet count and DIPSS category at baseline at a 2-sided Type I error level of 0.05. The log-rank test will provide 80% power to detect a hazard ratio of 0.54. Assuming a median survival time of 5.3 years for ruxolitinib plus placebo and enrollment duration is 1.5 years, the expected time to analysis from the first participant randomized is 3 years.

3.4. Schedule of Assessments

Refer to the Protocol for a full description of all study procedures and assessment schedules for this study.

4. DATA HANDLING DEFINITIONS AND CONVENTIONS

4.1. Scheduled Study Evaluations and Study Periods

4.1.1. Day 1

Day 1 is the date that the first dose of parsaclisib, placebo, or ruxolitinib is administered to the participants.

For randomized participants not treated with parsaclisib, placebo, or ruxolitinib, Day 1 is defined as the date of randomization.

4.1.2. Day 1 of Crossover for Crossover Participants

For participants who cross over from placebo plus ruxolitinib to parsaclisib plus ruxolitinib, Day 1 of crossover is the date the first dose of open-label parsaclisib is administered to the participants.

4.1.3. Study Day

If a visit/reporting date is on or after Day 1, then the study day at the visit/reporting date will be calculated as

$$\text{Day \#} = (\text{visit/reporting date} - \text{Day 1 date} + 1).$$

If the visit/reporting date is before Day 1, then the study day at the visit/reporting date will be calculated as

$$\text{Day \#} = (\text{visit/reporting date} - \text{Day 1 date}).$$

A study day of -1 indicates 1 day before Day 1.

4.1.4. Baseline Value

Baseline is the last nonmissing measurement obtained before the first administration of parsaclisib, placebo, or ruxolitinib.

For randomized participants not treated with any study drug, baseline is defined as the last nonmissing measurement obtained before the date of randomization for all parameters.

When scheduled assessments and unscheduled assessments occur on the same day and the time of the assessment or time of first dose is not available, use the following convention to determine baseline:

- If both a scheduled and an unscheduled visit are available on the day of the first dose and the time is missing, use the scheduled assessment as baseline.
- If all scheduled assessments are missing on the day of the first dose and an unscheduled assessment is available, use the unscheduled assessment as baseline.

